6.5 Subject Disposition

Enrolled

Individuals are considered enrolled if they have non-missing enrollment date. Enrolled individuals are referred to as “subjects”.

Completing the Open-label Treatment Phase

Subjects are defined as completing the open-label treatment phase if they complete the week 52 assessment, which means the subjects have completed the end of IP form and have eDiary data for the month 13.

Completing Study

Subjects are defined as completing the study if they complete the whole 64 weeks of study evaluation. It will be derived from the end of study CRF page with “completed” as the primary reason for ending study.

Exposed to Investigational Product

Subjects are defined as exposed if they receive at least one dose of investigational product in study 20130255.

6.6 Arithmetic Calculations

Exposure

For calculations of exposure, dose date refers to receiving dose > 0, but can include partial doses. The non-AE safety treatment group assignments will be based on the durations of IP exposure to AMG 334 70 mg and 140 mg as presented below (see also [Appendix C](#)).

Duration of IP Exposure for Subjects Receiving Only 70 mg or 140 mg

Duration = minimum (last dose date + 27, EOS date) – first dose date + 1.

Duration of IP Exposure for Subjects Receiving Both 70 mg and 140 mg

70 mg duration = minimum (first 140 mg dose date - 1, last 70 mg dose date + 27, EOS date) – first 70mg dose date + 1.

140 mg duration = minimum (last 140 mg dose date + 27, EOS date, date of data cut off) – first 140 mg dose date + 1.

Change from Baseline in Monthly Efficacy Measurement

The change from baseline in monthly efficacy measurement is the monthly efficacy measurement in **between consecutive exposures to IP** prior to the given time point minus the baseline monthly efficacy measurement (see Interval Based on Dose Dates for OLE Phase table presented in [Section 6.4](#)). For example, the change from baseline in monthly migraine days at week 12 will be calculated as:

(Monthly migraine days between week 12 interval start date and week 12 interval end date) – Baseline monthly migraine days

If the baseline or post-baseline value is missing, then the change from baseline is set to be missing.

Following efficacy endpoints will be calculated as above:

Secondary endpoints

- change from baseline in monthly migraine days
- change from baseline in monthly acute migraine-specific medication treatment in days
- **change from baseline in cumulative monthly headache hours**

Exploratory endpoints

- change from baseline in monthly migraine attacks
- change from baseline in monthly headache (migraine and non-migraine headache) days
- change from baseline in monthly moderate and severe headache (migraine and non-migraine headache) days
- change from baseline in monthly average severity of migraine pain
- change from baseline in monthly average severity of migraine related symptoms (nausea, vomiting, phonophobia, photophobia) for qualified migraine headaches
- **Change from baseline in migraine-specific quality of life, as measured by the MSQ, version 2.1**
- **Change from baseline in migraine-related disability, as measured by the MIDAS**
- **Change from baseline in pain interference with daily activities and migraine-specific impact, as measured by the PROMIS Pain Interference Scale short form and single pain and migraine symptom interference questions**
- **Change in physical impairment over time as measured by the MPFID**

- **Change in impact on everyday activities over time as measured by the MPFID**

Other endpoints

- change from baseline in monthly acute medication treatment in days
- change from baseline in monthly average migraine symptoms interference scale

Percent Change from Baseline

The change from baseline divided by baseline and multiplied by 100:

$$(\text{post-baseline} - \text{baseline}) * 100 / \text{baseline}$$

If the baseline value is 0, then the percent change from baseline is set to be missing. Percent change from baseline in monthly migraine days which is used to determine 50%, 75%, and 100% responder will be calculated as above.

Subject Incidence

The subject incidence for a given event in a given period is defined as the number of subjects with at least one reported occurrence of the event divided by the number of subjects who entered that period. For subjects with multiple occurrences of the same event, the event will only be counted once per subject.

Exposure-Adjusted Subject Incidence

The **exposure-adjusted subject incidence in a given period** is defined as the number of subjects with at least one reported occurrence of the event in a given time period of follow-up divided by total subject years of follow-up in that period. **For subjects with events, only the time until the first event contributes to the total subject years of follow-up. This rate will be presented per 100 subject years.** For subjects with multiple occurrences of the same event, the event will be only counted once per subject. Please refer to the table of safety analysis study windows in [Section 6.4](#) to calculate follow-up time in days for each subject.

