6.1 Definition of Terms Included in Study Endpoints

6.1.1 Safety Endpoints

Serious Adverse Event (SAE)

SAEs determined by the flag indicating if the adverse event is serious on the Adverse Events (AE) eCRF page will include those that occur after signing of the informed consent and up to and including end of study.

Treatment-Emergent Adverse Event

Adverse Events (AEs) recorded on the Adverse Events eCRF page that occur on or after first dose of investigational product as determined by the flag indicating if the adverse event started prior to the first dose on the Adverse Events eCRF and up to and including 112 days after the end of investigational product (16 weeks after the last dose of IP) or end of study, whichever comes earlier.

An AE that started in parent study 20120295 is only considered treatment emergent in the OLE study 20130255 if there is a worsening of the event. If the event is ongoing with no changes in severity, then it will not be considered an AE in 20130255.

Treatment-Related Adverse Event

A treatment-related AE is defined as a treatment-emergent adverse event that is considered by investigators to have reasonable possibility that it may have been caused by IP as determined by the flag indicating if the event is caused by investigational product on the Adverse Events eCRF page.

Columbia-Suicide Severity Rating Scale (C-SSRS)

The C-SSRS is a clinician rating of suicidal behavior and ideation. The version "Since Last Visit" will be used for this study. The C-SSRS consists of a maximum of 20 items to evaluate suicidal behavior and suicidal ideation. Please refer to [Appendix B](#) for more details.

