Study Phase	Start Time Point	End Time Point
Screening Phase for SAE only	Informed consent date	One study day prior to the first IP dose
Open-label Treatment Phase	Study Day 1 after the 1 st IP Dose	Min(EOS date, last IP dose date + 112 days)

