7.5 Pharmacokinetic/Pharmacodynamic Analyses Set

The pharmacokinetic analysis set will include all enrolled subjects in the safety analysis set who have at least one evaluable serum AMG 334 concentration post the first dose of IP. **Treatment group identifiers will be the same as the EAS.**

8. Interim Analysis and Early Stopping Guidelines

On an annual basis or until an administrative decision is made to close the study, descriptive statistics of safety and efficacy will be produced for use in the annual report and/or to support publications, if warranted.

An additional interim analysis may be performed for the purpose of inclusion in a regulatory submission to provide additional long-term safety data. This analysis may take place 4-6 months prior to the planned regulatory submission date (2Q 2017) and will include all safety data collected up to 01 September, 2016. There are no stopping rules applied based on any interim analysis and the outcome of this potential interim analysis will not lead to any changes in the conduct of the study.

Safety monitoring will occur in an ongoing fashion by the safety group.

The following summaries will be included for the interim analysis:

- Disposition, demographic, baseline characteristic and baseline disease characteristics, not including efficacy specific data, medical and surgical history, and important protocol deviations
- Adverse events
- Laboratory, vital signs, ECG, liver, antibody and C-SSRS
- Manufacturing lot numbers

9. Data Screening and Acceptance

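### At an interim or annual safety analysis, the AE follow-up window in SAP 6.4 has no data cut-off, so exposure-adjusted AE rates would include unobserved follow-up and be too low

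*SAP*

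**What the plan says.** SAP Section 6.6 defines exposure-adjusted subject incidence as subjects with the event divided by subject-years of follow-up, per 100 subject-years. For the follow-up days it directs the programmer to Section 6.4: "Please refer to the table of safety analysis study windows in" that section. The open-label row of that table ends the AE window at "Min(EOS date, last IP dose date + 112 days". The TEAE definition in Section 6.1.1 has the same two limits: "up to and including 112 days after the end of investigational product (16 weeks after the last dose of IP) or end of study", whichever is earlier. Neither mentions a data cut-off. Under Section 6.2 the EOS date is taken from the end-of-study eCRF page.

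Section 6.6 also gives durations of IP exposure, to be used for the non-AE safety grouping and, under Appendix C, the exposure summary:

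- One dose only: "Duration = minimum (last dose date + 27, EOS date) – first dose date + 1". No cut-off.
- Switchers, 140 mg period: "minimum (last 140 mg dose date + 27, EOS date, date of data cut off". This one has a cut-off.
- Switchers, 70 mg period: "minimum (first 140 mg dose date - 1, last 70 mg dose date + 27, EOS date". No cut-off, but the first 140 mg dose date limits it.

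Section 8 provides for annual descriptive safety summaries and allows an additional interim analysis for a regulatory submission. That interim "will include all safety data collected up to 01 September, 2016", and adverse events are among its listed outputs.

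**The concern.** At a data cut-off, a subject still on study has no end-of-study page and so no EOS date. The Section 6.4 minimum then reduces to the last dose plus 112 days, which lies after the cut-off for anyone still being dosed. Events are counted only up to the cut-off, but the denominator runs past it. The extra days can add no events, so the rate is biased downwards.

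Subject incidence of AEs is the primary endpoint, and Section 10.6.1 presents the AE summaries as exposure-adjusted rates. If the interim is run for a submission, these are the figures that regulators would see.

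**Working it through.** The plan states no figure for this point, so there is none to reproduce. The check applies the SAP's date rules as written and then with the cut-off added to the minimum.

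**Inputs.** The window end and duration formulas are those of SAP 6.4 and 6.6. Doses are 28 days apart, from study day 1 to day 337 (week 48), following the protocol's Schedule of Assessments. Assumption: when there is no EOS date, the minimum is taken over the remaining terms.

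**Excess per subject on monthly dosing.** Let d be the days from last dose to cut-off, from 0 to 27.

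- AE window: (last dose + 112) − (last dose + d) = 112 − d. This is 85 to 112 days, mean 98.5.
- Single-dose exposure: (last dose + 27) − (last dose + d) = 27 − d. This is 0 to 27 days, mean 13.5.

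**AE denominator for an event-free subject.** For a rare event, the change in rate is capped ÷ as written − 1.

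| Study day at cut-off | Last dose day | Capped (days) | As written (days) | Excess | Denominator | Rate |
|---|---|---|---|---|---|---|
| 182 | 169 | 182 | 169 + 112 = 281 | 99 | +54% | −35% |
| 252 | 225 | 252 | 225 + 112 = 337 | 85 | +34% | −25% |
| 364 | 337 | 364 | 337 + 112 = 449 | 85 | +23% | −19% |
| 400 | 337 | 400 | 449 | 49 | +12% | −11% |
| 448 | 337 | 448 | 449 | 1 | +0.2% | −0.2% |

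The last two rows are subjects in off-drug safety follow-up, where the excess runs down to nothing.

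**Cohort rates.** A subject's time at risk stops at the first event, so the excess is added only for those still event-free. With constant hazard h, observed follow-up t and window length s as written (both in years), the expected reported rate is

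Σ(1 − e^(−ht)) ÷ Σ[(1 − e^(−ht))/h + e^(−ht)(s − t)].

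For subjects at day 182 with h = 0.20 per year: t = 182/365.25 = 0.498 and s − t = 99/365.25 = 0.271. The numerator is 0.0949. The denominator is 0.4743 + 0.9051 × 0.271 = 0.7196. The reported rate is 13.2 per 100 subject-years against a true 20, or 34% too low.

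The documents give neither the entry pattern nor the hazard. Both are assumed below, with follow-up at cut-off spread evenly over the range shown and subjects complete from day 449.

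| Follow-up at cut-off (days) | True 2 | True 20 | True 100 | True 200 (per 100 subject-years) |
|---|---|---|---|---|
| 1–182 | −51.9% | −51.6% | −50.0% | −48.2% |
| 1–364 | −35.0% | −34.3% | −31.7% | −29.2% |
| 150–449 | −21.4% | −20.5% | −16.5% | −12.1% |
| 182–449 | −20.2% | −19.2% | −15.0% | −10.5% |
| 1–700 | −15.6% | −15.5% | −15.1% | −14.6% |

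The range is about 10% to 52% too low. In the second row, for example, a true 20 is reported as 13.1. With the cut-off in the minimum, the uncollected follow-up is zero in every case.

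**What the Section 6.6 formulas affect.** A single-dose subject spends 100% of exposed time on one dose whatever the duration, so the 80% grouping cannot change. The switchers' 70 mg period ends no later than the day before the first 140 mg dose. Once the switch has taken place, that date is observed, so no unobserved time enters.

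**The case against.** The strongest reply is that the SAP's stated scope in Section 1 is the final analysis, where every subject has an EOS date and the window is right. The submission interim is optional. Section 8 already restricts it to data collected by the cut-off, and follow-up or time at risk would not ordinarily be read to include days that have not happened. A careful programmer would cap the dates anyway.

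Part of this stands: the problem is conditional, and it disappears at the end of study. The rest does not remove it. Section 8 limits which data enter the analysis, but not a window end computed from the last dose date. Section 6.6 sends the programmer to the window table for follow-up time, and no section caps it; the cut-off date in Section 10.2 is only a table footnote. The cut-off in the switchers' 140 mg formula does nothing at the final analysis, so Section 6.6 was evidently written with earlier data cuts in view.

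The reply is also right that the larger percentages need short follow-up. Under SAP 3.1, subjects who started on 70 mg enrolled before Amendment 3, dated 31 March 2016. Read literally, they had at least 154 days by 01 September 2016, although later implementation at sites could shorten this. Section 11 expects most subjects to receive both doses. Both points make the top of the range less likely.

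**Conclusion.** The point holds for any interim or annual safety analysis at which some subjects have no EOS date. As written, the AE window adds 85 to 112 unobserved days per event-free subject on monthly dosing, and fewer for those in off-drug follow-up. The direction is clear: rates are too low. The size is not, because enrolment timing is not in the documents; 10% to 52% is the range over the assumed patterns, and no single percentage should be quoted as the bias. It also assumes that the formula is programmed literally.

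A reader might infer more than the documents support:

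- That the trial's final AE results are understated. They are not, because every subject then has an EOS date.
- That the single-dose exposure formula drives the AE rates. Those rates use the Section 6.4 window; the formula overstates exposure duration by at most 27 days per ongoing single-dose subject.
- That non-AE dose groups would be misassigned, or that the switchers' 70 mg formula has the same fault. Neither follows from the formulas.

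This should be corrected before any analysis at a data cut. It does not threaten the study's final conclusions.

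**What to change.** Make three one-term edits to the SAP:

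1. Section 6.4, AE window: end at the earliest of EOS date, last IP dose date + 112 days, and data cut-off date.
2. Section 6.1.1, TEAE definition: add the data cut-off date as a third limit, so that events and follow-up close on the same day.
3. Section 6.6, single-dose duration: add the data cut-off date to the minimum, as the switchers' 140 mg formula already does.

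Leave the switchers' 70 mg formula unchanged. The edits need no new data and do not change the final analysis. The cost is a small SAP revision and the matching change to the derivation programs.

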6.7 Disease Characteristics

Migraine-specific Medication

Migraine-specific medications include two categories of medications: triptan-based and ergotamine-based migraine medications **collected from subject's eDiary.**

Acute Headache Medication

Acute headache medication includes simple analgesics, combination analgesics, triptans, ergot-derivatives and opioids categories of medications.

Treatment Failure of Prior Migraine Prophylactic Medications

Treatment failure of prior migraine prophylactic medications is determined by “Reason for ending medication” as “Lack of efficacy” or “Adverse Reaction” in the Prior Migraine Prophylactic Medication parent study 20120295 eCRF page.

7. Analysis Subsets

7.1 Full Analysis Set

The full analysis set (FAS) includes all subjects who were enrolled in the study and received at least one dose of investigational product. Enrolled subjects must meet the study inclusion and exclusion. Presentation of disposition and baseline data will utilize this analysis set. **Treatment group identifiers, based on first dose received, will be as follows:**

- **AMG 334 70 mg**
- **AMG 334 140 mg**
- **AMG 334 Total**

7.2 Efficacy Analysis Set

The Efficacy Analysis Set (EAS) includes subjects who were enrolled and received at least one dose of IP and **had at least one change from baseline measurement in monthly migraine day** in study 20130255. **Subjects will be analyzed according to their randomized treatment group in the parent study 20120295 and the first dose received in the 20130255 OLE study, irrespective if a subject received only AMG 334 70 mg, 140 mg or both 70 mg and 140 mg in the 20130255 OLE study.**

Treatment group identifiers will be as follows:

- **Placebo / AMG 334 70 mg**
- **Placebo / AMG 334 140 mg**
- **AMG 334 70 mg / 70 mg**
- **AMG 334 70 mg / 140 mg**
- **AMG 334 140 mg / 70 mg**
- **AMG 334 140 mg / 140 mg**

Analyses for efficacy endpoints and patient reported outcomes (PROs) will utilize this analysis set except C-SSRS and MPFID.

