8. WITHDRAWAL FROM TREATMENT, PROCEDURES, AND STUDY

8.1 Subjects' Decision to Withdraw

Subjects have the right to withdraw from the study at any time and for any reason without prejudice to their future medical care by the physician or at the institution.

Subjects can decline to continue receiving investigational product and/or other protocol-required therapies or procedures at any time during the study but continue participation in the study. If this occurs, the investigator is to discuss with the subject the appropriate processes for discontinuation from investigational product or other protocol-required therapies and must discuss with the subject the options for continuation of the Schedule of Assessments ([Table 1](#)) and collection of data, including endpoints and adverse events. The investigator must document the change to the Schedule of Assessments ([Table 1](#)) and the level of follow-up that is agreed to by the subject (eg, in person, by telephone/mail, through family/friends, in correspondence/communication with other physicians, from review of the medical records).

Withdrawal of consent for a study means that the subject does not wish to receive further protocol-required therapies or procedures, and the subject does not wish to or is unable to continue further study participation. Subject data up to withdrawal of consent will be included in the analysis of the study, and where permitted, publicly available data can be included after withdrawal of consent. The investigator is to discuss with the subject appropriate procedures for withdrawal from the study.

8.2 Investigator or Sponsor Decision to Withdraw or Terminate Subjects' Participation Prior to Study Completion

The investigator and/or sponsor can decide to withdraw a subject(s) from investigational product and/or other protocol-required therapies, protocol procedures, or the study as a whole at any time prior to study completion.

Subjects may be eligible for continued treatment with Amgen investigational product(s) and/or other protocol-required therapies by a separate protocol or as provided for by the local country's regulatory mechanism, based on parameters consistent with [Section 12.1](#).

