40	Week 36 dose date; study day 253 if week 36 dose is not received (either missed or IP discontinued prior to week 36)	Week 40 IP dose date-1; study day 280 if week 40 dose is not received (either missed or IP discontinued prior to week 40)
44	Week 40 dose date; study day 281 if week 40 dose is not received (either missed or IP discontinued prior to week 40)	Week 44 IP dose date-1; study day 308 if week 44 dose is not received (either missed or IP discontinued prior to week 44)
48	Week 44 dose date; study day 309 if week 44 dose is not received (either missed or IP discontinued prior to week 44)	Week 48 IP dose date-1; study day 336 if week 48 dose is not received (either missed or IP discontinued prior to week 48)
52	Week 48 dose date; study day 337 if week 48 dose is not received (either missed or IP discontinued prior to week 48)	Study day 364

Note: for the intervals in month 6, 10, and 13 all available data before the next planned IP dose or visit should be used for calculation. Also refer to the definition of Monthly Migraine Days in [Section 6.1.2](#).

Study Visit

Since the actual visit for a subject may not exactly coincide with his/her targeted visit date, the actual visit date is mapped to the study visit as follows (visit windows below only apply to visits other than safety follow-up visit):

Study Phase	Study Visit	Target Day	Study Day
Open-label Treatment Phase	Day 1	1	1
	Week 4	29	2-43
n = 2 to 13	Week 4n	28n+1	28n-12 to 28n+15
	Week 8	57	44-71
	Week 12	85	72-99
	Week 16	113	100-127
	Week 20	141	128-155
	Week 24	169	156-183
	Week 28	197	184-211
	Week 32	225	212-239
	Week 36	253	240-267
	Week 40	281	268-295
	Week 44	309	296-323
	Week 48	337	324-351
	Week 52	365	352-379
	Safety Follow-up	The nominal visit from RAVE	

Note: If more than one visit (including the unscheduled visits, ie, CPEVENT='UNSCHED') fall within the same defined window, **scheduled visit will be used regardless of the distance from the target day. Unscheduled visit will only be used when there is no scheduled visit in the defined window.** The closest visit to the target day **among the same type of visit (scheduled vs. unscheduled)** will be considered for analysis. If two assessment dates are equidistant from the target date, the latter visit will be considered for analysis.

Above study visit table will be used for lab, vital signs, C-SSRS and PROs collected during office visit.

For adverse event, analysis windows will be set up based on study phase:

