10.1 General Principles

The final analysis for the entire study including open-label treatment phase and safety follow-up phase will be performed at the end of study.

All subjects who have enrolled and received at least one dose of AMG 334 in the study will be included in the data analysis.

For the purpose of secondary and exploratory efficacy endpoints in the 20130255 OLE study, the primary baseline is the 20120295 parent study baseline **(from the first day subject used eDiary in baseline at week -4 study visit through the day prior to**

study day 1). However, change from the parent study month 3 data may also be evaluated.

Efficacy endpoints will be summarized based on their randomized treatment group assignment in the parent study 20120295 **and the first dose received in the 20130255 OLE study.**

Summary descriptive statistics by each treatment group will be tabulated at each visit. For continuous endpoints number of observations, mean, median, standard deviation, first and third quartiles, minimum and maximum, and a two-sided 95% confidence intervals of the mean (except for safety laboratory analyses) will be included for descriptive statistics. For categorical and ordinal endpoints, the summaries will contain the number and percentage of subjects falling into each category.

No formal statistical tests will be performed. Missing values for safety endpoints will not be imputed.

The full analysis set will be utilized to summarize subject disposition of all enrolled subjects, demographic data, and baseline disease characteristics. The efficacy analysis set will be utilized to analyze efficacy endpoints. The SAS will be used to analyze safety endpoints, **which is the same as the FAS. The PRO analysis set will be used for the PRO substudy (ie evaluation of MPFID).**

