10.5 Efficacy Analyses

The analysis for efficacy endpoints will utilize the efficacy analysis set. Subjects will be analyzed according to their randomized treatment groups in the parent study 20120295 **and the first dose received in the 20130255 OLE study.**

For primary analysis of efficacy endpoints summary statistics on observed data are provided by visit and treatment group. Subgroup analysis of the secondary efficacy endpoints on observed data will be provided by sex, race, region and medication overuse, and by visit and treatment group.

PROs include PROMIS Pain interference, migraine symptom interference items, MSQ, **MPFID** and MIDAS. Change from baseline in total score (or subscale if applicable) of each PRO will be summarized descriptively on observed data by visit and treatment group. No sensitivity analysis will be conducted for PROs.

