10.7 Pharmacokinetic or Pharmacokinetic/Pharmacodynamic Analysis

The pharmacokinetic concentration will be summarized with descriptive statistics by visit and treatment group using PK analyses set. Treatment group assignments will follow those specified for the efficacy analysis.

11. Changes From Protocol-specified Analyses

Since most subjects are likely to receive both 70 mg and 140 mg in this study, descriptive summaries on efficacy endpoints will be presented by randomized treatment group in the 20120295 parent study and first dose received in this study, and not by maximum dose as described in the protocol.

Bed days and missed work/school days due to migraine symptoms not summarized since they were not summarized in 20120295 parent study.

12. Literature Citations / References

Fairclough DL1, Cella DF. Functional Assessment of Cancer Therapy (FACT G): non-response to individual questions. Qual Life Res. 1996 Jun;5(3):321-9.

13. Prioritization of Analyses

Summary tables of safety and efficacy will be produced for the use of the annual report and to support publications, if warranted. Therefore, they might be prepared earlier than others.

14. Data Not Covered by This Plan

There are no plans to specifically analyze or summarize the following data points. However, a listing of these data may be presented and/or additional exploratory analyses may be performed should inspection of the data warrant.

- ECG data
- general comments
- population pharmacokinetics
- biomarker

15. Appendices

[figure not shown]

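### The /70 mg efficacy and PK columns are starting-dose groups that can mix 70 mg, 140 mg and off-treatment data from month 2, and no efficacy or PK table in the SAP is by dose in force

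*SAP*

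**What the plan says.** SAP 7.2 defines six efficacy columns by crossing the parent-study arm (placebo, 70 mg, 140 mg) with the first dose in the extension (70 mg or 140 mg). Later dosing does not move a subject: the rule applies "irrespective if a subject received only AMG 334 70 mg, 140 mg or both 70 mg and 140 mg in the 20130255 OLE study". SAP 10.5 repeats it ("Subjects will be analyzed according to their randomized treatment groups in the parent study 20120295", together with first extension dose), and SAP 10.1 applies it throughout follow-up: "Summary descriptive statistics by each treatment group will be tabulated at each visit".

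PK follows the same rule. SAP 7.5 states "Treatment group identifiers will be the same as the EAS" and SAP 10.7 states "Treatment group assignments will follow those specified for the efficacy analysis".

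Under SAP 3.1, subjects already enrolled on 70 mg go up to 140 mg at the first possible visit among weeks 4, 8, 12, 16, 20, 24 and 28. Those already past week 28 stay on 70 mg. The protocol synopsis allows no step-down. SAP 11 replaces the protocol's maximum-dose grouping for efficacy and gives the reason: "Since most subjects are likely to receive both 70 mg and 140 mg in this study".

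Subjects off treatment can also stay in the columns. Protocol 8.1 says "Subjects can decline to continue receiving investigational product" while remaining in the study. The interval table in SAP 6.4 supplies calendar limits for that case; for example, the week 40 interval opens at "study day 253 if week 36 dose is not received (either missed or IP discontinued prior to week 36").

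**The concern.** A column headed by a dose is normally read as results at that dose. Here the three /140 mg columns hold one dose by plan, because no step-down is allowed. The three /70 mg columns do not: from the first switch visit they can hold subjects on 70 mg, subjects on 140 mg and subjects off treatment, with no count of each.

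What is at stake is interpretation. A reader looking for the concentration at 70 mg after a year, or for how well the effect on monthly migraine days holds up at 70 mg, would go to these columns and could be misled. PK is the clearest case, because concentration depends directly on the last dose. The reason given in SAP 11 refers to efficacy endpoints only; none is given for PK.

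The SAP already works by dose elsewhere. SAP 10.6.1.1 assigns adverse events to the dose at onset, and SAP 10.6 gives other safety data a separate 70/140 mg mixed group. The same 70 mg label would therefore mean different things in the safety tables and in the efficacy and PK tables of one report.

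**Working it through.** There is no stated figure to reproduce. The check sets the column rule against the switch schedule, the diary intervals and the PK visits.

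**1. Inputs.** Switch visits: weeks 4 to 28 (SAP 3.1). Reported efficacy months: 1, 2, 3, 6, 10 and 13 (SAP 6.1.2). The month 2, 3, 6, 10 and 13 intervals open with the week 4, 8, 20, 36 and 48 doses (SAP 6.4). PK visits: weeks 24, 52 and 64 (Protocol Table 1, by column position). At dosing visits the sample is taken before the dose (Protocol 7.2.1.9). The last scheduled dose is at week 48 (Protocol Table 1).

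**2. Number of 140 mg doses received, by switch visit.** Efficacy rows include the dose that opens the interval; PK rows count doses before the sample.

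| Switch at week | 4 | 8 | 12 | 16 | 20 | 24 | 28 |
|---|---|---|---|---|---|---|---|
| Month 2 | 1 | 0 | 0 | 0 | 0 | 0 | 0 |
| Month 3 | 2 | 1 | 0 | 0 | 0 | 0 | 0 |
| Month 6 | 5 | 4 | 3 | 2 | 1 | 0 | 0 |
| PK week 24 | 5 | 4 | 3 | 2 | 1 | 0 | 0 |
| Month 10 | 9 | 8 | 7 | 6 | 5 | 4 | 3 |
| Month 13 | 12 | 11 | 10 | 9 | 8 | 7 | 6 |
| PK week 52 | 12 | 11 | 10 | 9 | 8 | 7 | 6 |

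In a /70 mg column only month 1 is all 70 mg by plan. Month 2 is the earliest month that can be mixed. At month 6 and PK week 24 some switches may still lie ahead. By month 10 and PK week 52 none do.

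**3. Share on 140 mg.** The documents do not give it. Only 70 mg starters can receive both doses. If s is the share of all subjects who receive both and p the share who start on 70 mg, the switching share among 70 mg starters is f = s/p. If SAP 11's expectation means s > 0.5, then f > 0.5 among starters, because p cannot exceed 1. At a later visit 140 mg is the majority of the pooled /70 mg columns only if the retention of switchers, relative to all others in those columns, exceeds (1 − f)/f:

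- f = 0.51: 0.49/0.51 = 0.96
- f = 0.55: 0.45/0.55 = 0.82
- f = 0.60: 0.40/0.60 = 0.67
- f = 0.70: 0.30/0.70 = 0.43

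**4. Illustration for the week 52 mean concentration.** The safety margins in Protocol 2.3 imply 140:70 exposure ratios of 296/129 = 2.29 (AUC) and 275/111 = 2.48 (Cmax). Approximate dose proportionality above 70 mg (Protocol 2.2) gives 2.0. Let r be this ratio, w the share on 140 mg among treated subjects in the column, and g the share of sampled subjects off treatment, with concentration taken as 0. The column mean relative to a pure 70 mg mean is (1 − g)(1 + w(r − 1)). For r = 2.0 to 2.48:

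| w | g = 0 | g = 0.1 | g = 0.2 |
|---|---|---|---|
| 0.25 | 1.25 to 1.37 | 1.13 to 1.23 | 1.00 to 1.10 |
| 0.5 | 1.50 to 1.74 | 1.35 to 1.56 | 1.20 to 1.39 |
| 0.9 | 1.90 to 2.33 | 1.71 to 2.10 | 1.52 to 1.86 |

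The values of w and g are assumed. So is the step from Cmax and AUC to pre-dose concentrations. Exposure rises more than proportionally up to 70 mg (Protocol 2.2), so trough ratios may fall outside 2.0 to 2.48. The two departures pull in opposite directions, so a mean near the 70 mg value would not show that the column is pure.

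**5. Other tables.** Efficacy subgroups are sex, race, region and medication overuse (SAP 10.5). SAP 10.6.7 counts dose changes by treatment group, but within the safety analyses and not explicitly by visit. No efficacy or PK table is by dose in force.

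**The case against.** The case for leaving the plan alone is substantial. The change is declared in SAP 11 with a reason. SAP 5 describes a single-arm estimation study without hypotheses, the objectives concern AMG 334 and not a dose comparison, and PK is exploratory. The primary endpoint, adverse events, already has dose-at-onset tables. Starting-dose columns have stable membership over time. A by-dose efficacy table does not: after week 28, who is still on 70 mg depends on how far the subject had progressed when the increase came in, and pooling would mix parent-arm histories and 140 mg starters with switchers. All of this stands. It is why the first-dose efficacy tables should be kept and why a by-dose efficacy table can only be optional. It does not make the /70 mg cells readable by dose.

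A separate exposure-response supplemental plan is mentioned in SAP 9.7, for its software. It was not supplied, so whether it holds a by-dose PK summary cannot be judged.

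A reader might also infer that the protocol's maximum-dose grouping should be restored, or that it is useless. Neither follows. It applied to efficacy (Protocol 10.4.2) and safety (10.4.3), not specifically to PK. For subjects still on treatment at months 10 and 13 and PK week 52 it coincides with dose in force by plan. It mislabels 70 mg data as 140 mg only at visits before the switch, and it joins early stoppers with long-term 70 mg subjects.

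**Conclusion.** The point holds as one of interpretability. The first-dose grouping is a valid starting-dose summary, but /70 mg concentrations at weeks 24 and 52 and /70 mg efficacy at later months cannot be read as 70 mg results, and the tables carry no counts that would let a reader judge the mix. No test and no dose objective is affected.

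Three stronger readings are not supported:

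- That the /70 mg columns are in fact mixed from month 2. That is only the earliest month the schedule permits; actual switch dates are not given.
- That they are mostly 140 mg by months 10 and 13. SAP 11 states an expectation about subjects overall. It carries over to late visits only under the retention condition in step 3, and to each column separately only if enrolment timing was similar across parent arms.
- That the distortion has a known size. The PK ratios are illustrations under assumed shares, and no efficacy distortion can be calculated from the documents.

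What rests on no assumption is the schedule: planned switchers have had 0 to 5 doses of 140 mg before the week 24 sample and 6 to 12 before week 52, if dosing follows the plan. The correction is worth making because it is cheap and uses a principle the SAP already applies to adverse events.

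**What to change.** 1. **SAP 7.5 and 10.7.** Summarise the on-treatment PK samples (weeks 24 and 52) by the dose level of the last administration before the sample. Put subjects who missed the preceding scheduled dose or stopped treatment in a separate off-treatment row, so that early stoppers do not dilute a dose group. Show the number of 140 mg doses received before the sample. Summarise week 64 separately as post-treatment washout, by last dose level and time since last dose. If the exposure-response plan already contains this, a cross-reference is enough.
2. **SAP 7.2 and 10.5.** Keep the first-dose efficacy tables, label the columns as starting dose, and footnote each /70 mg column by visit with the numbers on 70 mg, on 140 mg and off treatment.
3. **Optional.** Add one supportive descriptive efficacy table by dose in force at the start of each interval, with off-treatment subjects separate. State that dose after week 28 depends on enrolment timing, that pooling mixes parent-arm history and 140 mg starters with switchers, and that the table does not support a dose comparison.

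The cost is SAP wording, footnotes, a PK regrouping and at most one extra table. No new data are needed. The drawbacks are some small cells and, in the optional table, changing column membership and the confounding just named.
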